9.3. Analysis of Outcome Measures

Data from all participants, excluding any that withdraw consent, will be used in the analysis. The primary outcome measure is the correlation between [A] ploidy status and [B] tumour: stroma ratio with local recurrence of cancer. Secondary outcome measures are i) correlation between [A] ploidy and [B] stroma analysis with overall survival after TEM surgery to remove rectal cancer, ii) the contribution of [A] ploidy and [B] stroma analysis to a regression model for local recurrence after TEM surgery to remove rectal cancer, and iii) Subgroup analysis comparing [A] ploidy and [B] stroma results with local recurrence and survival for patients who did and did not receive adjuvant chemo- or radiotherapy

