2. SYNOPSIS

Study Title	An observational study to correlate the results of ploidy and stroma analysis with prognosis in early rectal cancer	
Internal ref. no. (or short title)	Ploidy and stroma in early rectal cancer	
Study Design	Observational study	
Study Participants	Rectal cancer patients	
Planned Sample Size	150 patients	
Follow up duration	Minimum 18 months	
Planned Study Period	2 years	
	Objectives	Outcome Measures
Primary	To compare results of [A] ploidy and [B] stroma analysis with outcome after surgery to remove early rectal cancer	Correlation between [A] ploidy status and [B] tumour: stroma ratio with local recurrence of cancer
Secondary	
To compare results of [A] ploidy and [B] stroma analysis with survival after surgery to remove early rectal cancer
 
To assess predictive value of [A] ploidy and [B] stroma analysis for outcome after surgery to remove early rectal cancer
 
To compare results of [A] ploidy and [B] stroma analysis with outcomes by use of adjuvant treatment
	
Correlation between [A] ploidy and [B] stroma analysis with overall survival after TEM surgery to remove rectal cancer
 
Contribution of [A] ploidy and [B] stroma analysis to a regression model for local recurrence after TEM surgery to remove rectal cancer
 
Subgroup analysis comparing [A] ploidy and [B] stroma results with local recurrence and survival for patients who did and did not receive adjuvant chemo- or radiotherapy

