7.2. Inclusion Criteria

- Participant is willing and able to give informed consent (in English) for participation in the study, or gave informed consent for donation of tissue for research at the time of surgery.
- Male or Female, aged 18 years or above.
- Diagnosed with operable rectal cancer.
- Due to undergo, or has already undergone, TEM surgery to remove rectal cancer.
- A useable tissue sample has already been, or will be, taken as part of routine surgery.

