8.5. Data Handling

For Group A patients, who gave consent at the time of surgery, a member of the care team will extract the relevant data, including tumour characteristics, any (neo-)adjuvant treatment details and outcome information, identified only by MRN, from the TEM database. The care team member will then securely transfer this anonymised data, identifiable by MRN only, to the research team. The research team will then allocate each participant a study ID according to the recruitment log, and replace the MRN with the unique study ID. The transfer will be done using a password protected spreadsheet sent via encrypted email. For all other patients, who sign a specific study consent form, the researcher will prepare the data extract from the TEM database, identified only by MRN, and then replace the MRN with a study ID. The researcher will securely provide a list of MRNs, with date of surgery, to the pathology department. The MRNs will be linked to a unique study ID in a separate recruitment log.

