9.1. Description of Statistical Methods

All data will be stored in an Excel worksheet and analysed using Excel and R (a statistical programme).

The DNA ploidy results and tumour: stroma ratio will be correlated with local recurrence and survival. A subgroup analysis will additionally correlate ploidy and stroma with local recurrence and survival with and without adjuvant treatment.

A regression model will be developed incorporating ploidy and tumour: stroma ratio, along with a number of other known prognostic factors that are routinely collected, to assess whether ploidy and stroma have independent prognostic value in determining length of survival free of local recurrence, and length of disease-free survival.

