9.2. The Number of Participants

The study will recruit 150 participants, including both those who have already had surgery since 2007 and new patients having surgery after the study commences. Similar studies using these techniques of ploidy and stroma analysis compared to outcome after colorectal, breast and ovarian cancer that have produced significant results have generally used between around 150 and 300 patients [ref 3-6]. We expect to be able to recruit 150 patients, from amongst both those who have already had surgery and new patients, within a reasonable time-frame of 18 months.

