9.4. The Level of Statistical Significance

A 0.05 level of significance will be used.

9.5. Procedure for Accounting for Missing, Unused, and Spurious Data.

All available data will be used. Missing data will not be imputed. Spurious data will be re-checked, and if valid will be included in the analysis.

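### Overall survival is planned only as a correlation with each marker and has no age adjustment; the cost depends on age and marker patterns the documents do not give

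*Combined protocol and SAP*

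**What the plan says.** Section 9.3 lists as secondary outcome i the "correlation between [A] ploidy and [B] stroma analysis with overall survival after TEM surgery to remove rectal cancer". Section 5 times it from surgery to death and does not restrict the cause. Section 9.1 also says only that the markers will be correlated with survival. No test, model or covariate is named for overall survival.

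The plan has one adjusted analysis, a regression described in section 9.1, whose purpose is "to assess whether ploidy and stroma have independent prognostic value in determining length of survival free of local recurrence, and length of disease-free survival". Section 9.3 describes that regression as a model for local recurrence alone. Neither section applies it to overall survival. Its covariates are unnamed prognostic factors already in routine collection.

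Age appears only as an eligibility criterion: "Male or Female, aged 18 years or above" (section 7.2), with no upper limit. The extract in section 8.5 covers "the relevant data, including tumour characteristics, any (neo-)adjuvant treatment details and outcome information". That list is open-ended, so it allows age but does not name it.

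**The concern.** After removal of an early cancer, many deaths may have nothing to do with the tumour, and age is then likely to be a main driver of death from any cause. Section 4 notes that earlier stroma studies used only cancer-related death, so the issue matters more here. Surgery goes back to 2007, and section 12.7 expects some patients to have died.

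Two separate problems can follow from leaving age out. If the marker is unrelated to age, the comparison is less powerful than the data allow. If the marker varies with age, part of the age effect is reported as a marker effect, or a real marker effect is hidden. The study's purpose is to improve advice to patients on prognosis, so a survival result that cannot be separated from age is of limited use.

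**Working it through.** **Inputs from the documents.** Sample size: "The study will recruit 150 participants" (section 9.2). Significance: "A 0.05 level of significance will be used" (section 9.4); sidedness is not stated, and two-sided is assumed. Follow-up: "Minimum 18 months" (section 2), with surgery since 2007. Adding the planned two-year study period to the protocol date of October 2016 gives October 2018, so January 2007 to then is at most about 11.8 years.

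**No planned figure to reproduce.** Section 9.2 rests the sample size on precedent, namely that similar studies "have generally used between around 150 and 300 patients". It gives no effect size, power, event count or marker prevalence. For scale, Schoenfeld's formula gives the hazard ratio (HR) detectable at 80% power as exp[(1.96 + 0.84) / √(d·p·(1−p))], where d is deaths and p the marker share. With d = 45 and p = 0.5 this is exp(2.80 / 3.35) = 2.31. Power for HR 2.0 is Φ(3.35 × 0.693 − 1.96) = Φ(0.365) = 64%. Over 20–60 deaths and shares of 30–50%, power for HR 2.0 runs from 30% to 77%. There is little to spare.

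**Simulation, with assumptions not taken from the documents.** Age mean 70, SD 11; death hazard 3.5% per year at age 70; marker prevalence 45%; censoring uniform over 1.5–11.8 years; age HR 1.04–1.10 per year (1.04^10 = 1.48 and 1.10^10 = 2.59 per decade). Cox models with and without age were fitted to 1,500 cohorts per setting. The simulation error of a rejection rate near 50% is √(0.5 × 0.5 / 1500) = 1.3 points. True HR 2.0 gives about 42–49 deaths.

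| Marker and age | Age HR per year | True marker HR | Unadjusted | Age-adjusted |
|---|---|---|---|---|
| (a) Unrelated | 1.04 | 2.0 | power about 3 points lower | reference |
| (a) Unrelated | 1.07–1.10 | 2.0 | HR 1.73–1.89, power 45–55% | HR 2.01–2.05, power 64–66% |
| (b) Prevalence rises 5 points per decade | 1.04–1.10 | 1.0 | 5–9% false positives | about 4–6% |
| (b) Prevalence rises 10 points per decade | 1.04–1.10 | 1.0 | 7–22% false positives | about 4–6% |
| (c) Prevalence falls 5 points per decade | 1.04–1.10 | 2.0 | power 25–45% | power 58–64% |

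**What the slopes mean.** The mean age difference between marker groups is slope × SD² / [p(1−p)]. Five points per decade gives 0.005 × 121 / (0.45 × 0.55) = 2.4 years, and ten points gives 4.9 years. With no true effect, the unadjusted HR is roughly exp(age difference × log age HR). At 2.4 years and 1.04 per year that is exp(2.4 × 0.039) = 1.10, which matches the simulated 1.10.

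**Second check with a different set-up.** Marker share 40%, follow-up 1.5–10 years, within-group age SD 10, age HR 1.5, 2.0 and 2.5 per decade.

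- Age unrelated to the marker, true HR 2.0: power 61%, 62% and 55% unadjusted, against 62%, 69% and 69% adjusted. The loss is about 2, 7 and 14 points, the first within simulation error.
- No true effect, marker-positive group 3 years older: HR 1.11, 1.21 and 1.25; false positives 5.0%, 9.7% and 11.3%.
- No true effect, 5 years older: HR 1.22, 1.36 and 1.51; false positives 8.6%, 15.6% and 23.1%. Adjusted, these six settings give 4.0–6.1%.
- True HR 2.0, marker-positive group older: the unadjusted HR reads 2.24–2.61 and rejects in 76–94% of runs, against 62–67% adjusted. The extra rejections come from upward bias.

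The two set-ups show the same pattern.

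**The case against.** The strongest reply is that the objective is to compare the markers with survival, and an unadjusted association answers that. Where age is unrelated to the marker, the unadjusted hazard ratio nearer 1 is a marginal quantity, different from the age-conditional one and not an error. This stands. It is why the unadjusted result should stay, and why the case under (a) is about power and not bias.

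The sections also name no method, so they never say that the analysis must be unadjusted. That is true, but a plan that names no covariate for overall survival does not provide age adjustment either. Age may be among the unnamed prognostic factors in section 9.1, but that model is for other endpoints. The open-ended extract list may also cover age, so the documents do not show that age is unavailable.

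The size of harm is open to challenge. With an age effect of 2% per year the power loss is about 1 point. With 9% per year but prevalence rising only 2 points per decade, the unadjusted HR is 1.07 and false positives are 6.1%. Adult eligibility says nothing about the actual spread of ages.

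A reader might infer that the survival result will both lose power and show a false effect wherever a marker varies with age. The documents do not support that. The two harms need different conditions, a false effect of any size needs a strong age effect and a sizeable imbalance together, and no section says that either marker varies with age.

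Finally, adjusting for age alone leaves out tumour size, depth and lymphatic invasion. Whether a marker adds to pathology is a further question; age is the minimum for death from any cause.

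**Conclusion.** The omission is clear from the text: overall survival has no age adjustment as written, and the only adjusted model is directed at other endpoints. What it costs cannot be known from the documents, which give no age distribution, marker prevalence, death count or marker–age association. It ranges from negligible, when the age effect is weak and the groups are similar in age, to material in either direction: up to about 19 points of power lost under (a), up to 22% false positives under (b), and power as low as 25% under (c). These three outcomes are alternatives and should not be added together.

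The change is worth making because it costs little and held up in every setting tried: the adjusted estimate stayed close to the true value, and false positives stayed near 5%. The outcome is secondary, and the primary analysis of local recurrence is not affected.

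**What to change.** 1. In sections 8.5 and 10.3, name age at surgery in whole years (not date of birth) as an item in the extract for all groups. Do this before extraction, since records are then re-labelled with study IDs and going back becomes harder.
2. In section 9.3, state that overall survival will be analysed with a Cox model for each marker, with age at surgery as a continuous term, and that the unadjusted hazard ratio will be reported alongside. Any further covariates should be few, named in advance and in keeping with the expected number of deaths.
3. While editing, reconcile sections 9.1 and 9.3 on which endpoints the regression model covers.

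The cost is one extra column and a sentence or two of text. There is no new procedure for patients, and age in whole years adds little to identifiability.

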9.4. The Level of Statistical Significance

A 0.05 level of significance will be used.

9.5. Procedure for Accounting for Missing, Unused, and Spurious Data.

All available data will be used. Missing data will not be imputed. Spurious data will be re-checked, and if valid will be included in the analysis.

9.6. Inclusion in Analysis

All patients who consent to the study will be included in the analysis.

9.7. Procedures for Reporting any Deviation(s) from the Original Statistical Plan

Not applicable. The analysis involves only simple statistical measures of readily available data.

10. DATA MANAGEMENT

10.1. Source Data

Source documents are where data are first recorded, and from which participants' CRF data are obtained. These include, but are not limited to, hospital records (from which medical history and previous and concurrent medication may be summarised into the CRF), clinical and office charts, laboratory records, diaries, radiographs, and correspondence.

CRF entries will be considered source data if the CRF is the site of the original recording (e.g. there is no other written or electronic record of data). All documents will be stored safely in confidential conditions. On all study-specific documents, other than the signed consent, the participant will be referred to by the study participant number, not by name.

10.2. Access to Data

Direct access will be granted to authorised representatives from the Sponsor and host institution to permit study-related monitoring, audits and inspections.

10.3. Data Recording and Record Keeping

For Group A patients who consented at the time of surgery, a member of the care team will prepare a data extract for all participants from the TEM database, in the form of an Excel spreadsheet, and securely transfer this anonymised data, identifiable by MRN only, to the research team. The research team will then allocate each participant a study ID according to the recruitment log, and replace the MRN with the unique study ID. For all other patients, who sign a specific study consent form, the researcher will prepare the data extract from the TEM database, identified only by MRN, and then replace the MRN with a study ID. All subsequent study data will be entered into the Excel spreadsheet. Data from this study will be generated at the Oxford University Hospitals and Institute for Cancer Genetics and Informatics, Oslo. Data will be analysed at the Oxford University Hospitals by the research investigators. Personal data will be stored and accessed by the investigators for less than 3 months. Research data will be stored for 10 years after the completion of the study.

The participants will be identified by a unique study specific number in the study database. For those who previously consented for tissue donation the MRN will be linked to the unique study number in the recruitment log. All other participants who consent will also be assigned a unique study identifier linked to their personal information. The name and any other identifying detail will NOT be included in any study data electronic file.

All electronic data will be password-protected and anonymised. All hard copy files and data will be kept in a locked cabinet within a locked office with restricted access. Access to the data will be restricted to study team members. The NHS Code of Confidentiality will be followed. This study will follow the sponsor organisation's policy regarding data storage and the NHS Code of Confidentiality. Information derived from the study will be stored on a single, secure (password encryption) NHS computer. This will be positioned within a secure location in the hospital.

Participants will be informed using patient information sheets of how data will be stored (only participants who did not sign a tissue donation form at the time of surgery will receive patient information sheets). The principal investigators will constantly review the security of research data files.

11. QUALITY ASSURANCE PROCEDURES

The study will be conducted in accordance with the current approved protocol, GCP, relevant regulations and standard operating procedures.

The study may be monitored or audited in accordance with the current approved protocol, GCP, relevant regulations and standard operating procedures.

12. ETHICAL AND REGULATORY CONSIDERATIONS

12.1. Declaration of Helsinki

The Investigator will ensure that this study is conducted in accordance with the principles of the Declaration of Helsinki.

12.2. Guidelines for Good Clinical Practice

The Investigator will ensure that this study is conducted in accordance with relevant regulations and with Good Clinical Practice.

12.3. Approvals

The protocol, informed consent form and participant information sheet will be submitted to an appropriate Research Ethics Committee (REC), the Confidentiality Advisory Group (CAG) and host institution(s) for written approval.

The Investigator will submit and, where necessary, obtain approval from the above parties for all substantial amendments to the original approved documents.

12.4. Reporting

The CI shall submit once a year throughout the clinical study, or on request, an Annual Progress Report to the REC, host organisation and Sponsor. In addition, an End of Study notification and final report will be submitted to the REC, host organisation and Sponsor.

12.5. Participant Confidentiality

The study staff will ensure that the participants' anonymity is maintained. The participants will be identified only by a participant ID number on all study documents and any electronic database. All documents will be stored securely and only accessible by study staff and authorised personnel. The study

will comply with the Data Protection Act, which requires data to be anonymised as soon as it is practical to do so. No participant will be identified in any publication of the results in any way.

12.6. Expenses and Benefits

No visits additional to normal care are anticipated, so there is no expectation of patients incurring any expenses.

12.7. Other Ethical Considerations

The majority of potential patients will have consented to tissue donation and anonymous use, and use of anonymous data for research at the time of surgery. In order to link the tissue and data, the tissue must be made identifiable. It is not feasible to contact this participant group for consent to link the data and tissue; as the surgical procedures date back to 2007, many potential participants may have moved from the Oxford area and some may be deceased. The data and sample will be linked using the hospital MRN number. This is a trust-specific reference number outside the OUHFT participants are not identifiable by this number. Once linked the data and samples will also be re-anonymised (or linked anonymised). There will be no onward disclosure of patient data outside the care team, as the researcher is also part of the participants' care team.

Tissue samples will be transferred outside the UK. A material transfer agreement will be in place to cover the terms of the transfer of the samples to the Institute of Cancer Genetics and Informatics in Oslo. The samples will be identifiable by study ID only, when they are transferred to Norway. Participants consent to the transfer of their linked anonymised samples to Norway.

13. FINANCE AND INSURANCE

13.1. Funding

Internal funding from Nuffield Division of Clinical and Laboratory Sciences, Oxford will cover the costs of retrieving the pathology specimens, and from the Institute for Cancer Genetics and Informatics, Oslo will cover the processing and analysis of the specimens.

13.2. Insurance

NHS bodies are legally liable for the negligent acts and omissions of their employees. If you are harmed whilst taking part in a clinical study as a result of negligence on the part of a member of the study team this liability cover would apply.

Non-negligent harm is not covered by the NHS indemnity scheme. The Oxford University NHS Trust, therefore, cannot agree in advance to pay compensation in these circumstances.

In exceptional circumstances an ex-gratia payment may be offered.

14. PUBLICATION POLICY

An observational study to correlate the results of ploidy and stroma analysis with prognosis in early rectal cancer

IRAS reference: 195159 REC reference: 16/WM/0443

CONFIDENTIAL

Date and version No: 21 October 2016 v1.1

Page 14 of 16

The Investigators will be involved in reviewing drafts of the manuscripts, abstracts, press releases and any other publications arising from the study. Authors will acknowledge the source of funding for the study. Authorship will be determined in accordance with the ICMJE guidelines and all other contributors will be acknowledged.

16. APPENDIX A: AMENDMENT HISTORY

Amendment No.	Protocol Version No.	Date issued	Author(s) of changes	Details of Changes made

Protocol amendments must be submitted to the Sponsor for approval prior to submission to the REC committee.
